### IRB Amendment #9072- 7/14/2020

This following portion of the amendment is addressing changes to our protocols due to the COVID-19 virus. We were in the middle of the study at the time of the pandemic. We halted data collection and recruitment. We are expecting some of our sites to be open to visitors soon (per our Ohio researcher partners, July 1, 2020) and this amendment is preparing for resumption of month 6 data collection for existing subjects; and continued recruitment and enrollment (and other study activities) for new sites. We expect Michigan sites to allow us to resume later but these changes will apply there as well as sites open up. List of changes:

- 1) We will be submitting letters/emails from the Long-Term Care Communities where research activities are taking place as we receive them and visitor restrictions are lifted. We will only reengage in research activities after communicating with each site, sharing our COVID-19 prevention procedures, reviewing and training our data collectors on the community specific COVID-19 prevention procedures, and receiving notice that we may re-enter the community.
- 2) We will provide the attached COVID-19 handout and discuss with the participant and/or their LAR the following information. After reviewing the handout with the participant and/or their LAR, we will ask if they would like to continue in the study.
- 3) All study staff will complete the applicable modules of the CDC Nursing Home Infection Preventionist Training Course ([https://www.train.org/cdctrain/training\\_plan/3814](https://www.train.org/cdctrain/training_plan/3814)) prior to reengaging in research activities. Modules to be taken include: Infection Prevention and Control Program, Principles of Standard Precautions, Principles of Transmission-Based Precautions, Hand Hygiene, Respiratory Hygiene and Cough Etiquette, Environmental Cleaning and Disinfection.
- 4) SOPs for study staff related to COVID-19 and accompanying documents include the following: a) Study Staff Screening and Reporting (Screening Tool attached): Study staff will be required to use the attached screening log (individual) each day prior to entering the community. Study staff will take a picture of the log and send to the site coordinator each day before entering. The Site Coordinator will use the department log to record all study staff self-assessments. b) Disinfection equipment (Checklist attached): All equipment will be disinfected prior to entering the community as well as in between participant visits. c) PPE, distancing, and hygiene: Study staff will follow the CDC recommended precautions to reduce the spread of COVID-19 (covering cough/sneeze with tissue or crook of elbow, frequently washing hands for 20 seconds, using >60% alcohol-based hand sanitizer, etc.). Study staff will not visit any other buildings/LTC community sites prior to entering the current community for the day. Study staff will be provided 2 cloth masks that will be doffed prior to entering the community each day. Study staff will change clothes once leaving the building and put those clothes, as well as their mask, in a plastic bag to wash each night when they return home. Staff will keep 6 feet of distance except during the transfer of research material (COVID-19 Handout, Informed Consent, and Montreal Cognitive Assessment), when pushing a wheelchair, or when a participant feels unsteady during wayfinding. d) Meeting space and participant flow management: For the assessment portion of data collection, participants will be asked to come to a designated room in each community where the meeting space (i.e. table) is disinfected after each participant visit. Study staff will not meet or visit participants in their rooms. In order to reduce risk of exposure to both the study staff and communities, one data collector will be assigned per community for data collection and will wait 2 weeks after completing data collection in one community to enter into another community.

### **IRB Amendment #10128 - 9/29/2022**

We are requesting to expand our data collection visit windows. Currently, we visit our study sites post intervention at Months 1, 3, 6, and 12. The visit windows for these visits are one week prior to - one week after month 1; and 2 weeks prior to - 2 weeks after months 3, 6 and 12. At this time, we have baseline data in 3 new sites, and have instituted our intervention. We have found out that due to COVID, some sites are required to close for 10 days at a time (for example, if there is an exposure, or if someone tests positive). Then the sites do test 29 of all residents and staff during that time. We (and other visitors) are usually not allowed in and we also have specified in our protocol that we do not go into sites if they are closed to visitors.

Thus, to avoid missing data in sites, we propose to expand our visit windows to one month prior to the next visit window for visits 1, and 6 and for one month after Month 12. We will keep the other visits on the current timeline (not expanding the length of the trial). Thus, for example, if a site is closed for two weeks during Month 1; we will have until one month before Month 3 to collect Month 1 data.

We are hoping we won't have to do this often, but we have no way of predicting what will happen with COVID. This will allow us to continue the trial and get longitudinal data. The statistician has been consulted to assist us with dealing with the varying timelines. Dates are collected for each measurement time period.

## Statistical Analysis Plan

**Management and Analysis.** The data will be entered into the study database, cleaned and assessed for completeness. Then the data will be de-identified and transferred into SAS 9.4 statistical software for analysis.

**Preliminary analysis.** The distributions of outcomes and control variables will be summarized. For continuous outcomes, normalizing transformations will be applied as needed. If they are not successful, then the modeling approach will involve generalized linear models with the appropriate error distribution (e.g., gamma or beta). Since the level of randomization is facility and the unit of analysis is individual, the appropriate random effects will be specified in all statistical models to account for nesting of individuals within facilities.

**Analysis of feasibility measures.** Attrition rates and reasons and baseline measures of the dropouts will be compared by trial arm to ensure absence of attrition bias. Resident responses to the acceptance of cues questionnaire and staff responses to the interview questions will be summarized overall, by trial arm (cues only versus cues + spaced retrieval education), and by care community. The staff focus group data will be transcribed into *Atlas Ti* and analyzed using constant comparison analysis. Text will be chunked into common units and assigned a code. Codes will be grouped into like categories (axial coding) and then like categories will be assigned themes. Similarities and differences of themes among the arms and care communities will be summarized.

**Primary analysis.** The primary analysis will follow the intent to treat approach and will include all participants as randomized.

**Specific Aim 1** examines the effect of salient cues with and without spaced retrieval education on wayfinding ability. The statistical model #1 for the repeated measures of wayfinding ability at 1, 3, 6, and 12 months will include the following explanatory variables: wayfinding ability at baseline, time (with levels 1, 3, 6, 12 months), trial arm, and control variables measured at baseline (see the measures section). Time will be included as categorical variable with the above mentioned levels to model potentially non-linear (polygonal) changes in outcomes over time. For the first measure of wayfinding ability, average speed calculated as described in the measures section, this model will be implemented as a linear mixed effects (LME). It will also include random effect indicating facility as will all other statistical models. The LME model generalizes classical analysis of repeated measures and allows for data missing at random, time-varying covariates, and structured covariance matrix. The participants who completed at least one post-baseline assessment will be included in the analysis following the intent to treat principle. The second measure of wayfinding ability, the proportion of wrong turns, by definition takes values from the [0, 1] interval and will be analyzed using generalized LME with beta distributed errors. Beta distribution supported on [0, 1] interval is particularly suitable to this measure.

The essential parameter of interest in the statistical model #1 is associated with the trial arm variable. The least square (LS) means corresponding to this variable will be output from the model, and differences among them will be tested. The test of significance of the differences between LS means for cues versus control and cues + spaced retrieval education versus control will yield the formal test of hypothesis H01. The test of the significance of the differences between cues + spaced retrieval education versus cues alone will yield the formal test of hypothesis H02. After testing the main trial arm effects, time by trial arm interaction will be added to the statistical models to explore whether intervention effects change as time progresses. The significance of the interaction term will be assessed, and differences in LS means by trial arm at each time point will be tested to determine the immediate and sustained effects.

**Specific Aim 2** tests the effect of the active trial arms on the secondary outcome of life space. Statistical model #1 will be modified to include the repeated measures of life space as the

dependent variable, and hypothesis H03 will be tested by comparing the LS means for the two active arms. This will first be done using *Tinetti's Nursing Home Life-Space Diameter* measure for all participants.

**Handling of missing data and alternative analytical approaches.** The patterns of missing data will be evaluated using SAS PROC MI to determine if the assumption of missing at random (MAR) is reasonable. The analysis techniques for Aims 1-3 allow for MAR mechanism. If patterns of missing data indicate potential missing not random (MNAR) mechanism, then models describing missing mechanisms will be considered (e.g. pattern-mixture models). Since MNAR or MAR assumptions are not directly testable, we will employ sensitivity analyses to investigate how the results would or would not change under pattern-mixture or other models for the missing mechanism.

**Strategies for Multiple Inferences.** Because the study hypotheses were stated a-priori, adjustments for multiplicity are not necessary in the analyses for the main study Aims 1 and 2. In additional analyses for the exploratory Aim 3, false discovery rate will be controlled using Hochberg or Benjamini-Hochberg procedures. Since adjustments for multiplicity are controversial, the results will be presented both unadjusted and adjusted.

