## 6. Purpose of Research

The overall goal of this project is to assess the contribution of cues and spaced retrieval education on wayfinding ability and life space in persons with wayfinding impairment who live in long term care communities in a randomized controlled trial. We will select nine senior assisted living residences and recruit 137 residents identified as having wayfinding problems who can move themselves and communicate. We will randomize the facilities to one of three arms 1) Control (no changes); 2) Cued (salient environmental landmarks and signage placed at key decision points) plus staff training on use of the cues and 3) Cued plus Spaced- Retrieval education. Subject characteristics including mobility, demographic variables, activities of daily living, and cognitive ability will be measured along with life space mobility (spatial extent of mobility). We will test all subjects' wayfinding ability (primary outcome) and life space (secondary outcome) at baseline and at 1, 3, 6, and 12, months. We will compare wayfinding performance over time among the 3 trial arms.

The specific aims are:

Aim 1: To examine the effect of salient cues with and without spaced retrieval education on wayfinding ability initially and over time in older adults who have wayfinding deficits in long term care communities. HO1: Subjects will have improved wayfinding (faster, more accurate) in the cued condition versus the control condition at months 1, 3, 6, and 12; and post intervention compared to pre intervention.

H02: Subjects in the cued condition + Spaced Retrieval education will have improved wayfinding ability compared to the control and cue alone condition at times 1, 3, 6, and 12 months.

Aim 2: To determine the effects of salient visual cues and spaced retrieval training on life space.

H03: Subjects in the cued conditions will have larger life spaces than those in the control condition at times 1,3, 6 and 12 months.

H04: Wayfinding ability will be positively correlated with larger life space over time.

Exploratory Aim 3: To determine which subject characteristics are most amenable to the intervention; and which subject characteristics place persons at risk for less responsiveness to the intervention so that the intervention can be appropriately targeted.

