2. The IL communities will be randomly assigned to waves 1, 2 or 3 (three per wave). The AL communities will be assigned to wave
3. Three routes, which vary with respect to complexity (low, medium, and high complexity), will be chosen based on the space syntax assessment for each community using a computer program that calculates space syntax. Space syntax gives numerical values of complexity for routes in terms of length of path, number of path intersections, visibility of destinations, connectedness of spaces (direct connection versus indirect connection through intermediate spaces) and salience of existing cuing

(number, size, contrast, location and distinctiveness of cues). The rationale for choosing the routes based on space syntax is so that similarly complex routes can be compared among communities with different building design, and so that a range of complexity of routes is provided.

4. Subjects will be recruited and enrolled from each of the three communities prior to the intervention (see Human Subjects section).

5. After enrollment, the care communities will be randomized to either the control (Arm 1), Cued (Arm 2) or Cued Plus SR (Arm 3) condition. The rationale for randomizing after enrollment is to reduce potential selection bias due to the type of participants that agree to be in the study based on being in the intervention group or not.

6. At baseline, all enrolled subjects will undergo measurements of wayfinding ability, health, cognition, mobility and life space.

7. Arms 2 and 3 of the will have salient visual cues (colorful, familiar objects), including pictures, signage, statues and nature elements placed throughout the care community at key decision points (Figure 1). Arm 3 will additionally receive SR education, which uses a procedural memory cue over increasingly longer spaces of time. The control care communities will receive no change in décor or training (described below).

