#### Study Outcomes (Dependent Variables)

Primary Outcome: Wayfinding Performance. Wayfinding is the ability of participants to find their way to key locations and back to the starting point (bedroom, dining area; and back to starting place).

Wayfinding performance will be measured at times 0, 1, 3, 6 and 12 months using the method of Brush

et al. Subjects will be asked to show the route from his or her bedroom to Location 1: from the Location 1 to the Location 2; and from Location 2 to the participant's. Two research assistants will walk with the participant to obtain the following measures:

- 1) Time to move from one location to another/distance. Time will be measured for each of the three routes along with the total distance in (feet/yards) of the path. The average speed of covering this distance will be calculated as  $v = (\text{total distance}) / (\text{total time})$ , thus standardizing variation in distance and the resulting time that could be present among different care communities. If elevators are present, time will be stopped once the participant reaches the elevator and uses it, and time measurement will be resumed upon exiting the elevator. If subjects make a wrong turn, they will be corrected and 2 minutes added for each time they are corrected.
- 2) Errors are defined as the percent of errors made (wrong turns) based on the number of possible turns. Depending upon the route selected by the subject, the number of possible turns is variable so that the percentage of wrong turns will be calculated.

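### The beta model planned for the proportion of wrong turns cannot use error-free walks (exact 0), and the SAP gives no rule for values of 0 or 1

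*SAP*

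**What the plan says.** The Protocol (8d, Study Outcomes) has two measures of wayfinding, the primary outcome: average speed and errors. On the second it says: "Errors are defined as the percent of errors made (wrong turns) based on the number of possible turns". It adds: "Depending upon the route selected by the subject, the number of possible turns is variable". Step 3 of 8d says: "Three routes, which vary with respect to complexity (low, medium, and high complexity), will be chosen". Neither document says whether turns are pooled over these routes.

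The SAP (Specific Aim 1) places the proportion in the closed interval from 0 to 1, says that it "will be analyzed using generalized LME with beta distributed errors", and gives the reason: "Beta distribution supported on [0, 1] interval is particularly suitable to this measure". The arm contrasts from this model are the formal tests of H01 and H02. H01 (Protocol, section 6) reads in part: "Subjects will have improved wayfinding (faster, more accurate) in the cued condition versus the control condition".

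On the analysis set, the SAP says under Primary analysis that the analysis "will include all participants as randomized", and under Specific Aim 1: "The participants who completed at least one post-baseline assessment will be included in the analysis following the intent to treat principle".

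**The concern.** The measure is a ratio of counts. A participant who makes no wrong turn scores exactly 0, and that is the best result the cues can produce. The beta likelihood breaks down at exactly that value, so the interval given as the reason for the model includes the two points where it fails.

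Nothing elsewhere fills the gap. The distributional fallback under Preliminary analysis concerns continuous outcomes and names gamma and beta as examples; gamma also excludes 0. The missing-data section does not cover observed boundary values.

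Zeros are plausible. One of the three routes is of low complexity. The inclusion criteria (Protocol 8a) require impairment at baseline, whereas the modelled outcomes are at months 1 to 12. If the cues work, zeros should be more common in the active arms.

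The stake is the accuracy part of H01, and H02 for the same measure. Dropping end-point records selects on the outcome, and a participant whose follow-up walks were all error-free would leave the analysis. Adding an offset keeps everyone, but the arm estimate then depends on a constant that is not prespecified.

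**Working it through.** The plan gives no figure to reproduce on this point. The check has three steps.

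**1. The likelihood at the end points.** For shape parameters a and b, the log-density is (a−1)log(y) + (b−1)log(1−y) − log B(a,b).

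| a, b | y = 0 | y = 1 |
|---|---|---|
| 2, 8 | −∞ | −∞ |
| 0.5, 4.5 | +∞ | −∞ |
| 1, 9 | 2.197 | −∞ |

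The value at 0 is finite only when a is exactly 1, and at 1 only when b is exactly 1. When the shapes are estimated, an end-point record has no usable contribution.

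**2. How often an exact 0 could occur.** The documents give no error rate, turn count or spread between people. All of the following are assumptions: mean error 20% in control and 10% in cued, T possible turns, and a beta-binomial with a+b = 10. The shapes are then (2, 8) and (1, 9), and P(0) = B(a, b+T)/B(a, b).

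- T = 12, control: (8×9)/(20×21) = 72/420 = 17%.
- T = 12, cued: 9/21 = 43%.
- T = 36 (for example, three routes of 12 pooled), control: 72/(44×45) = 72/1980 = 4%.
- T = 36, cued: 9/45 = 20%.

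Exact values of 1 are negligible here.

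**3. What each way of handling them does to the arm effect.** The true log-odds ratio is log(0.20/0.80) − log(0.10/0.90) = −1.386 + 2.197 = 0.81. A beta regression (arm effect on the logit mean, common precision) was fitted by maximum likelihood to the exact beta-binomial distributions. It covers one visit, with no facility effect and no baseline covariate. Offsets use y(1−2d)+d. Compression uses (y(n−1)+0.5)/n, with n = 114, or n = 456 for 114 × 4 visits.

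| Case | Records at 0 or 1, control / cued | Drop | Offset d = 0.0001 / 0.001 / 0.01 | Compression n = 114 / 456 |
|---|---|---|---|---|
| T = 12, a+b = 10 | 17% / 43% | 0.33 | 0.73 / 0.69 / 0.62 | 0.65 / 0.69 |
| T = 36, a+b = 10 | 4% / 20% | 0.52 | 0.92 / 0.83 / 0.70 | 0.76 / 0.83 |
| T = 36, a+b = 1000 | 0.0% / 2.4% | 0.77 | 0.88 / 0.85 / 0.77 | 0.81 / 0.84 |

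Over a grid of T = 8, 12, 20, 36 and a+b = 5, 10, 1000, with the same means, 2% to 59% of cued records lie at an end point. Dropping gives 0.23 to 0.77, offsets give 0.48 to 1.02, and compression gives 0.49 to 0.91.

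**The case against.** - **The SAP leaves room to adapt.** It says that distributions will be summarised first, and its list of alternative error distributions is open, so a zero-inflated or binomial form could be adopted later. That is a third route besides dropping and offsetting. But the text concerns continuous outcomes whose transformation fails, it states no rule for boundary values, and Specific Aim 1 commits this measure to beta. A choice made after the zeros are seen is what prespecification is meant to prevent.
- **The quoted sentence is not literally false.** The support of a beta distribution is commonly written as the closed interval. This is fair as a matter of wording. The failure is in the likelihood at observed end points.
- **The magnitudes rest wholly on assumptions.** This stands. Offsets can push the estimate either way, and the effect nearly disappears when zeros are rare. If the arms share the same distribution, any fixed rule gives an expected arm effect of zero, so the threat is to estimation and power more than to false positives. What remains is freedom to choose the rule after seeing data.
- **The intent-to-treat text is about participants, not records.** This also stands. The text is contradicted outright only when all of a participant's follow-up walks are at an end point.
- **The point is limited.** This is one of two wayfinding measures, the sample size rests on wayfinding time, and the Protocol describes a pilot trial. These facts bound the importance, but the measure still carries a formal test.

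**Conclusion.** The concern holds. The analysis stated for a formal test of H01 and H02 fails as soon as one walk is error-free, and no rule covers that case. This follows from the outcome definition and the form of the likelihood, and needs no assumption about frequency beyond a zero occurring. In practice the problem is at 0.

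The size of the effect on the arm contrast is unknown. The figures above are illustrations and not an expected bias: they show that the choice of rule can matter a good deal (0.33 to 0.73 against 0.81 in the 12-turn case) or little (0.77 to 0.88 at 36 turns with a+b = 1000). The average-speed tests and the sample size are not affected. The point should be fixed before analysis.

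**What to change.** Replace the beta model with a binomial mixed model for wrong turns out of possible turns (logit link; beta-binomial if overdispersed), with participant and facility random effects. Delete the sentence on the suitability of the beta. State whether the three routes are pooled. State also that each possible turn is counted at most once, which the SAP's own range of 0 to 1 already implies.

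This model has one drawback: walks with more possible turns get more weight, and the Protocol lets that number depend on the route the subject selects. An unweighted comparison of proportions can be reported as a sensitivity analysis.

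If a beta form is kept, prespecify one of two options:

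- a zero/one-inflated beta model, naming the combined arm contrast that tests H01 and H02; or
- a fixed compression rule, with its formula and n, plus a sensitivity analysis on the constant.

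The cost is SAP wording and model syntax. Both counts are already needed to form the percentage. The lightest version, a fixed compression rule with its sensitivity analysis, takes a few sentences.

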**Please provide justification for why the number of subjects to be recruited is appropriate.**

The sample size for this study was determined based on Specific Aim 1, Hypotheses H01 and H02 for the pairwise comparisons of the trial arms. In the prior R15-funded study of the PI, the effect size for the difference in wayfinding time observed under cue versus no cue condition was 0.42 (a reduction of 8 minutes on average, with a standard deviation of 19 minutes). In the proposed study, wayfinding will be measured at baseline, 1, 3, 6, and 12 months. Since baseline measure will be used as a covariate in the analysis of repeated measures of outcomes (see the analysis section), the adjusted standard deviation in this analysis would be smaller than unadjusted. Assuming correlation of 0.4 between pairs of repeated measures, the effect size adjusted for the design of the proposed trial and analysis strategy is 0.67, which would be detected with power 0.8 or greater in two-sided tests using 0.05 level of significance with the sample size of 36 per group. Next, this sample size was adjusted to account for clustering of participants within care communities using a conservative estimate of the intraclass correlation coefficient (ICC) of 0.0012. The resulting design effect factor is 1.042 yields the sample size requirement of 38 per group, or 114 total. Finally, to account for projected 20% attrition, 137 participants will need to be recruited. This corresponds to the average recruitment goal of 11 participants per care community. The participating care communities stated that they have 10 to 30 available participants satisfying the inclusion criteria; therefore the required sample size is feasible.

**Briefly describe the subject population characteristics (i.e., age ranges, and where appropriate, gender, ethnic background, and health status).**

Planned enrollment includes men and women 62 years and older. For NIH our enrollment table includes an ethnic and racial mix of subjects in alignment with the population in the cities in which the study is being conducted - however, the sample is a convenience sample.

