Secondary Outcome: Life Space. Life space is defined as the spatial extent of mobility within an environment, and varies from a small life space (limited to one's room) to a large life space (travels outside of the care community). Life space will be measured using a modified version of Tinetti's Nursing Home Life-Space Diameter at times 0, 1, 3, 6, and 12 months. The tool is a survey that asks subjects or their caregivers to state how often per day (in the past 2 weeks) an individual moves within spaces, including their own rooms, outside the room but within the unit/hallway/floor, outside the unit/hallway/floor but within the care community, and outside the care community. Frequency is rated on a scale from 0 = never to 5 (> 3 times/day) for each level of life space. Scores for each life space are summed, with the total ranging from 0-50 and higher scores representing more mobility and a larger life space. Tinetti reported test-retest reliability of the measure with  $r=.922-951$  using different nurse raters.

A weakness of Tinetti's tool is the reliance on self-report; thus we will use an electronic tracking device to measure life space on a subsample of subjects for one community from each of the arms for years 2-4 of the study (one community for each Arm; Y2 = Arm 1; Y3=Arm2; and Y4 = Arm 3). Tracking devices have been used in healthcare and manufacturing for years, but have only recently been used in long term care. Primarily they have been used to identify when individuals with dementia elope from buildings or areas. Except for one small study involving hard wired monitoring devices, mobility tracking has not been used to measure life space. There is at least one system available that provides a wearable technology (wristband) and "anchors", which are devices that plug into the community's wall outlets. The system uses Bluetooth to identify the participant's location inside to a location to accuracy within 10 feet. The system provides real time tracking and reporting which can be used to track life space. Secure data is stored in the cloud. Because this technology is relatively new, we did not want to rely on it solely. But it would give a much more accurate and detailed report of locational information than the Tinetti measure and provide valuable information about the effect of cues on life space.

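### Read literally, the Aim 2 life-space model keeps baseline wayfinding and never names baseline life space as a covariate, which would usually cost precision for H03

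*SAP*

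**What the plan says.** The SAP, under Specific Aim 1, lists the explanatory variables of model #1 as "wayfinding ability at baseline, time (with levels 1, 3, 6, 12 months), trial arm, and control variables measured at baseline". Under Specific Aim 2 it adapts that model to the secondary outcome: "Statistical model #1 will be modified to include the repeated measures of life space as the" dependent variable. No baseline life-space term is mentioned, and the SAP does not say whether baseline wayfinding is dropped.

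The missing covariate is collected. The protocol (section 8d, Study Outcomes) has life space measured with the modified "Nursing Home Life-Space Diameter at times 0, 1, 3, 6, and 12 months", and step 6 of section 8d includes life space in the baseline assessment of every enrolled subject. It does not enter by another route: neither the covariates named under Measures nor the list under Control Variables contains it.

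The nearest statement of general strategy is in the sample-size justification (protocol section 7a): "Since baseline measure will be used as a covariate in the analysis of repeated measures of outcomes", the adjusted standard deviation is expected to be smaller. That paragraph sizes the trial for H01 and H02, which concern wayfinding.

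**The concern.** A subject's starting level on an outcome usually predicts the later level on the same outcome well, and the plan's own sizing relies on this for wayfinding. A life-space model that carries another outcome's baseline and not its own would normally have more residual variance than it needs.

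Facilities are randomized, and there are few of them: four per arm if the 12 communities of section 8d divide equally, three if the nine named in section 6 are used. Chance differences in starting life space between arms are therefore quite possible, and the literal model has no term that adjusts for them directly.

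The literal model is also not fully defined. Wayfinding has two measures, speed and proportion of wrong turns, and nothing says which baseline would be carried into the life-space model. If the covariates are not fixed in advance, they could be chosen after the data are seen.

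**Working it through.** **Inputs from protocol section 7a (all for wayfinding)**
- Unadjusted effect size: it "was 0.42 (a reduction of 8 minutes on average, with a standard deviation of 19 minutes"; 8/19 = 0.421.
- "Assuming correlation of 0.4 between pairs of repeated measures".
- Result: "the effect size adjusted for the design of the proposed trial and analysis strategy is 0.67", detected with "power 0.8 or greater in two-sided tests using 0.05 level of significance with the sample size of 36 per group".

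**Step 1. Reproduce the plan's figure.** Take the mean of the four post-baseline visits, unit variance at each visit, and a common correlation ρ between all pairs of measurements.
- Variance without the baseline: (1 + 3ρ)/4 = (1 + 1.2)/4 = 0.55.
- Variance adjusted for the outcome's own baseline: 0.55 − ρ² = 0.55 − 0.16 = 0.39.
- Adjusted effect size: 0.42/√0.39 = 0.673, which the plan gives as 0.67.
- A two-sample t-test with effect size 0.67 needs 36 per group (power 0.8005).

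So the plan's sizing is reproduced by own-baseline adjustment. Without it, the wayfinding effect size would be 0.42/√0.55 = 0.566, power at 36 per group about 66%, and the requirement 50 per group.

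**Step 2. Apply the same structure to life space.** The documents give no correlation of life space over 1 to 12 months. The test-retest figure in Study Outcomes is a reliability obtained with different nurse raters and is not a substitute. ρ for life space is therefore an assumption. So is r, the correlation of baseline wayfinding with each later life-space measurement.
- Adjusting for baseline life space: V_own = (1 + 3ρ)/4 − ρ².
- Adjusting for baseline wayfinding instead: V_way = (1 + 3ρ)/4 − r².
- Standard-error ratio: √(V_way/V_own).

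| ρ (life space) | r | V_way | V_own | SE ratio |
|---|---|---|---|---|
| 0.4 | 0 | 0.55 | 0.39 | 1.19 |
| 0.4 | 0.2 | 0.51 | 0.39 | 1.14 |
| 0.4 | 0.3 | 0.46 | 0.39 | 1.09 |
| 0.4 | 0.4 | 0.39 | 0.39 | 1.00 |
| 0.2 | 0 | 0.40 | 0.36 | 1.05 |
| 0.6 | 0 | 0.70 | 0.34 | 1.43 |

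**Step 3. Allow for the control variables.** The table gives them no explanatory value. As an illustration, assume the retained covariates explain 20% of single-visit variance through stable differences between persons, with ρ = 0.4. The single-visit variance becomes 0.8 and the covariance between visits 0.4 − 0.2 = 0.2.
- Without baseline life space: 0.55 − 0.20 = 0.35.
- With it: 0.35 − 0.2²/0.8 = 0.35 − 0.05 = 0.30.
- SE ratio: √(0.35/0.30) = 1.08.

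None of these figures includes clustering by facility.

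**The case against.** The best defence is that the SAP says the model will be modified, not that only one element changes. The sentence on baseline covariates in section 7a speaks of outcomes in general and points to the analysis section. Model #1 already serves two wayfinding measures under one generic baseline term, so it can be read as a template in which each outcome takes its own baseline. This makes a swap to baseline life space a plausible intention. It does not make it a specification: the section 7a sentence belongs to the wayfinding sample size, and the SAP does not carry it into Aim 2.

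A reader might infer something stronger: that the plan has decided to exclude baseline life space, and that H03 thereby loses the equivalent of 29% of participants (1 − 0.39/0.55) or has only 66% power. The documents do not support that. They leave the covariate unstated and do not record a decision against it. The 29% and 66% assume that baseline wayfinding and every control variable say nothing about later life space. Yet H04 expects wayfinding and life space to be related, and ADL, mobility aids and cognition are all in the model. The power figure also borrows wayfinding's effect size and group size, and no effect size or power target is set for life space. Nor would baseline imbalance pass wholly unadjusted into the arm contrast, because those related control variables remain.

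The objection that this is a secondary outcome in a self-described pilot trial limits the consequence. It does not remove the reason to fix the covariates in advance.

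**Conclusion.** The point holds as one of specification and probable lost precision. Taken at its word, the Aim 2 text yields a model with baseline wayfinding and without baseline life space, and the SAP gives no statement to the contrary.

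At an assumed within-outcome correlation of 0.4, the cost in standard error runs from about 19% when baseline wayfinding is uninformative, to 9% when it correlates 0.3 with later life space, to nothing when that correlation matches life space's own. The 19% is close to an upper bound at that correlation. With baseline wayfinding uninformative, the cost is about 5% at a correlation of 0.2 and 43% at 0.6. Informative control variables would reduce any of these, and clustering is left out throughout.

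No bias or type I error problem is shown, and the primary wayfinding analysis is unaffected.

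**What to change.** State in the SAP, under Specific Aim 2, that the model has life space at 1, 3, 6 and 12 months as the dependent variable and includes baseline life space as a covariate. State also whether baseline wayfinding is retained as an additional covariate or replaced. If it is retained, name which wayfinding measure is used.

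Dropping baseline wayfinding is not needed to obtain the gain, and the plan itself expects it to relate to life space, so either choice is defensible if prespecified. The change is one sentence, needs no new data, and costs at most one degree of freedom.
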